## 5. BRAIN12-IMPLEMENTATION PROCEDURE

### 5.1. STUDY ENROLLMENT METHOD AND FEASIBILITY

Use of the biomarkers GFAP and UCH-L1 being part of the 2023 guidelines for management of mTBI in Spain, and being now included in the new clinical management pathway in the hospital 12 de Octubre, all patients with mTBI admitted to the ER of the study site and answering to inclusion and exclusion criteria of the study will be considered for participation in this study. All patients assessed for mTBI will be considered for inclusion in the mTBI management bundle. This bundle of care, already accepted in the Department will include obtention of blood biomarkers by venepuncture. Patient management will not be altered by the study. De-identified patient data will be obtained from the clinical records and will be studied. All data obtained is recorded for the normal management of mTBI patients and therefore no extra information will be obtained. No further contact with the patient will be made outside of their normal interactions at the Hospital and with their general practitioner. Records from the electronic clinical records will be the only source of data in this study both in the acute setting and in the follow up of the patients.

## 5.2. STUDY TIMELINE AND PLANNED MANAGEMENT ALGORITHM

All patients with TBI admitted to the ER and with a GCS between 13 and 15 will receive a blood test for biomarker determination upon admission. All patients with GCS of 13 or with a focal neurological deficit on admission will receive a CT. CTs could be performed to GCS14 and 15, independently of the result of the combined test, but the results of the test will be taken into consideration to guide for prescribing a CT. The attending physician will be responsible for the management of the patient and will have to determine the reason to prescribe CT despite normality of the biomarker test. The management algorithm that is recommended is as follows:

Risk factors (RF) include:

- Loss of consciousness.
- Posttraumatic amnesia (anterograde or retrograde).
- Advanced age (over 65)
- Antithrombotic treatment including platelet inhibitors.
- Difficulty in assessing level of consciousness: Cognitive impairment, intoxication.
- Persistent symptomatology: Repeated vomiting, persistent headache.
- High energy or High-risk mechanism: Falls over one's height, car accident, pedestrian involved in traffic accident, or accidents in which other there are other seriously injured patients.

Data will be collected directly from a specified structured form in the electronic health record of the patient. All data will be pseudonymised. Information regarding follow up will be recorded from the electronic health record regarding new contacts with the hospital or need of further assessment.

### 5.3. PARAMETER ASSESSMENTS

#### 5.3.1. Clinical parameters

1) Vital signs will be measured in the emergency department according to standard practice (GSC score, arterial blood pressure, heart rate, respiratory rate, body temperature, pulse oximetry). The presence of vomiting, nausea or headache will be recorded, as well as the presence of loss of consciousness. All recorded variables will be obtained following the standard of care of the workup of the mTBI patient established in the Hospital and no extra information will be obtained.

Secondary deterioration within the first week after TBI will be obtained by reviewing electronic medical history of the patient's and new contacts during this week with the ER, and is defined as follows:

- a decrease in GCS score of more than 2 points from the initial GCS score in the absence of sedatives
- a deterioration in neurologic status sufficient to warrant intervention, i.e. mechanical ventilation, sedation, osmotherapy, neurosurgical procedure or admission to the intensive care unit.
- Admission to a hospital ward exclusively related to deterioration of neurological condition due to TBI.

### 5.3.2. Biological assessments (BA)

Blood samples will be drawn only for the management of patients with mTBI, as established by the mTBI care bundle and within 12 hours after TBI. The volume of blood collected will be that necessary to obtain results for both GFAP and UCH-L1 biomarkers. Permission for obtention of this blood sample will follow the normal standard of care of any other blood sample obtained in the ER. For normal health care management of patients admitted due to mild TBI in which a CT scan is going to be performed, laboratory analysis regarding hemogram and formula, coagulation status (Prothrombin time (PT), INR and aPTT) and conventional biochemistry analysis (Na, K, glycemia, creatinine, AST and ALT) are normally obtained by local laboratories as a standard of care. These data of the conventional laboratory analysis performed to these patients as standard of care will be obtained and stored in the eCRF.

### 5.3.3. DATA COLLECTION AND DATA MONITORING

Data obtained as standard of care for the management of mTBI will be collected in the electronic clinical records. The Electronic Health Record is an essential tool for clinical decision-making and data collection, as it enables accurate and systematic documentation of patient information. However, its full potential is exploitable and useful when the data is structured. For this reason, and since the TBI information will be collected in the HER(Electronic Health Record), the hospital's IT data area improved the structuring and standardization of the information in the EHR. To this end, the mTBI diagnostic code was unified and codified (SNOMED CT) and a form was created with the questions that are asked when attending a patient with TBI. The completeness of the defined diagnosis together with the designed form will allow the identification of the cohort of patients with mTBI. In addition to the data included in the form, the study will collect demographic and baseline information at admission, the reason to prescribe brain CT scan and immediate CT findings by the local radiologist, biological data if indicated by the in-charge physician.

At 10 days postTBI, clinical research associates will review all information regarding the neurological status of the patients and the need for hospitalisation or other contacts to the ER in relation to mTBI. This review will be done thanks to the previous automatic extraction of the mTBI data collected in the EHR.

Regular quality checks on the information consigned in the EHR by attending physicians will be performed as a program for quality improvement of mTBI bundle. This program has been already run by the Department of Neurosurgery in order to enhance the recording of structured data in clinical records in our hospital. For this purpose, a dashboard in Power Business Intelligence (PowerBI) has been designed. In addition to functioning as an instrument for monitoring data recording, this PowerBi dashboard will also show the indicators outlined below for the purpose of protocol evaluation. These are time of care in the emergency department for patients with mTBI, percentage of CT requested, percentage of CT requested

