## BRAINII2-IMPLEMENTATION STUDY

positive (beyond the threshold concentration). This test has been already tested in a large number of European patients and has presented good safety and reliability profiles.

To determine the safety of the new protocol all information regarding the neurological status of the patients in relation to mTBI will be analyzed up to two weeks after the mTBI, specifically neurological deterioration, need for further observation of the patient or admission or need for treatment(medical or surgical) related to mTBI.

In order to determine the reduction of CT scans obtained with this new protocol, absolute numbers and proportions of patients finally scanned using this new protocol will be compared to the reference management of a similar number of patients during a similar historical period(i.e. data from the previous six month for patients attended for mTBI at Hospital 12 de Octubre).

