## BRAIN12-IMPLEMENTATION STUDY

- a) The presence of a plausible traumatic mechanism as described by the patient's recount of the injury event.
- b) Presence of one or more clinical signs attributable to brain injury: Loss of consciousness immediately following injury, alteration of mental status immediately following the injury, posttraumatic amnesia or any neurological abnormality.
- c) At least two acute symptoms related to the injury: feeling confused or disoriented, headache, nausea, vomiting, dizziness, vision problems, memory problems, emotional lability or irritability.
- e) GCS between 15 and 13, assessed at least 30 minutes after injury.

-Blood sample obtained ≤12 h after injury and before any imaging prescription.

Patients will not be included in the new pathway if:

- GCS 3-12 on admission
- Time of injury unknown
- Time to injury exceeding 12 hours
- Primary admission for non-traumatic neurological disorder (e.g., stroke, spontaneous, intracranial hematoma)
- Penetrating head trauma
- Patient with mechanical ventilation from the trauma scene or prehospital management.
- Venipuncture not feasible

Participation in the study will not affect patient management.

[figure not shown]

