## BRAINII2-IMPLEMENTATION STUDY

in patients with negative biomarkers, percentage of CT requested in patients with positive biomarker, percentage of pathologic CT in patients with positive biomarker, percentage of pathologic CT in patients with negative biomarker, percentage of patients requiring admission and percentage of second ED visit after discharge.

Finally, the de-identified data from the mTBI cohort will be obtained and transferred into a web based electronic CRF(eCRF) built on RedCap to be able to be analysed. The database in RedCap will contain pseudo-anonymised clinical information about the patients with mTBI from six months prior to the implementation protocol and information from six months of the implementation protocol.

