## 6. STUDY STOPPING RULES

### 6.1. STUDY STOPPING CRITERIA FOR A PARTICIPATING SUBJECT

Participants will be excluded from the study and replaced in case of a violation of an inclusion criterion, e.g. in the mTBI group: no mild TBI, no CT scan when the patient should have received one according to the study design, no blood sampling or after 12 hours post-injury.

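### Principal objective 3 compares CT proportions on different denominators: sampling and replacement rules select new-period patients but cannot act in the same way on the reference group

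*Protocol*

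**What the plan says.** **What is compared.** Section 3.2 states that "absolute numbers and proportions of patients finally scanned using this new protocol will be compared to the reference management". Section 1 lists this as principal objective 3. Costs (Section 3.3.2) and time differences (Section 1) are also set against the historical group.

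**New period.** Section 4.1 requires "Blood sample obtained ≤12 h after injury and before any imaging prescription". Section 1 gives the same criterion but softens the imaging part with the word *ideally*. Section 4.1 also keeps patients out of the pathway for "Venipuncture not feasible". Under Section 6.1, participants are taken out and replaced for, among other reasons, "no blood sampling or after 12 hours post-injury", and also when they were not scanned although the design called for a scan.

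**Reference period.** Section 3.2 describes "a similar number of patients during a similar historical period" and explains this as "data from the previous six month for patients attended for mTBI at Hospital 12 de Octubre". It states no inclusion criteria, GCS range or 12-hour window for this group. Age matching appears only for costs.

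**How patients are found.** Section 5.3.3 reports that "the mTBI diagnostic code was unified and codified (SNOMED CT) and a form was created", and that the coded diagnosis and the form together identify the cohort. No start date is given. One database is to hold "clinical information about the patients with mTBI from six months prior to the implementation protocol" together with the six months of implementation.

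**The concern.** A before-after comparison of proportions means something only if the same kind of patient can enter both denominators. Biomarker sampling belongs to the new pathway, so reference patients cannot meet or fail the sampling rules. A patient in the new period who is never sampled leaves numerator and denominator, while the same patient six months earlier would have stayed in both.

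Two of the rules also touch the outcome being compared. Read literally, Section 4.1 makes a patient ineligible if CT is ordered before the blood is drawn. Section 6.1 removes patients who were not scanned when a scan was due.

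At stake is the estimate of CT reduction. It could reflect who was counted rather than what the pathway changed. Costs and times use the same two groups, so they have the same problem, though the protocol gives no figures from which to size it there.

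**Working it through.** **Plan's own figure.** The only sample-size count that can be reproduced is 1000 × 0.10 = 100 CT-positive patients (Section 7.1). Nothing is calculated for objective 3: no reference CT rate, expected reduction or unsampled share is given. The CT rates and unsampled shares below are therefore assumptions.

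**Step 1. The rules side by side.**

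| Rule | New period | Reference period |
|---|---|---|
| Sample within 12 h | required (1, 4.1) | cannot apply |
| Sample before imaging is ordered | required (4.1); *ideally* (1) | cannot apply |
| Venipuncture feasible | required (1, 4.1) | cannot apply in the same way |
| Removed if unsampled or sampled late | yes (6.1) | cannot apply |
| Removed if not scanned when due | yes (6.1) | not stated |
| GCS 13-15, injury within 12 h, clinical criteria | required (1, 4.1) | not stated |
| Unified code and form | yes (5.3.3) | not stated |

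**Step 2. Can unsampled patients arise?** Section 5.2 says every patient with GCS 13-15 is tested. Section 8.1 makes sampling depend on the attending physician's clinical indication. About 1000 tests are expected. The stated volumes are 3000 a year (Section 1) or 3500 a year with suspected TBI (Section 7.1), that is 1500 or 1750 in six months. Tested patients are then 1000/1500 = 66.7% or 1000/1750 = 57.1% of that volume. Some of the remainder may not meet the mild TBI criteria, so this gap is an extreme case.

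**Step 3. Spurious change from dropping unsampled patients, with no true effect.** Let r be the CT rate among all patients (the same in both periods), u the unsampled share in the new period and c the CT rate among the unsampled. The new-period proportion becomes (r − u·c)/(1 − u). With r = 0.70 and u = 0.15:

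- c = 0.95: (0.70 − 0.1425)/0.85 = 0.656, a 4.4-point reduction.
- c = 0.40: (0.70 − 0.06)/0.85 = 0.753, a 5.3-point increase.

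Over a range of u, as new minus reference in percentage points:

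| u | c = 0.95 | c = 0.40 |
|---|---|---|
| 5% | −1.3 | +1.6 |
| 10% | −2.8 | +3.3 |
| 15% | −4.4 | +5.3 |
| 30% | −10.7 | +12.9 |

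If c = r, the spurious change is zero.

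**Step 4. Scale.** The 95% half-width for 1000 versus 1000 at 70% is 1.96 × √(2 × 0.7 × 0.3/1000) = 4.0 points.

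**Step 5. Extreme case from the stated volumes.** If the reference took all 1500 or 1750 patients, the spurious difference would be (1 − s) × the gap in CT rate between tested and untested patients, where s is the tested share. A 10-point gap gives 0.333 × 10 = 3.3 or 0.429 × 10 = 4.3 points. A 20-point gap gives 6.7 or 8.6. The sign follows the sign of the gap.

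**Step 6. The not-scanned-when-due rule.** It takes only unscanned patients out of the new-period denominator, so it raises that proportion. If it removed 5% of patients (assumed) at r = 0.70, the result would be 0.70/0.95 = 0.737, an increase of 3.7 points.

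**The case against.** Several points on the other side have force.

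- **Broader denominator.** Section 1 words the measure as CTs prescribed for mTBI patients over the study period, not for sampled patients. The dashboard in Section 5.3.3 lists overall CT requests apart from those split by biomarker result. The authors may therefore intend an all-patient denominator. But the inclusion criteria and Section 6.1 apply to the study as a whole, and nothing exempts objective 3.
- **Code and form.** A reader might infer that the reference patients were found without the unified code and form. The protocol does not say so. Section 5.3.3 describes both as already created, does not tie them to one period and puts both periods in one database, which is compatible with a single extraction. Section 11 places technology deployment in January-March 2025, just before an April start, but does not say whether code or form was part of it. The supportable statement is that coverage of the reference window is not given.
- **Direction.** A reader might infer that the design flatters the new pathway, because patients sent straight to CT drop out. That is one possibility. Section 5.3.2 says routine bloods are normally taken when a CT is planned, so the unsampled may instead be low-risk patients who are seldom scanned. The not-scanned-when-due rule also pushes the proportion up.
- **Before imaging.** This is firm in Section 4.1 only. Section 1 softens it, and Section 6.1 does not list sampling after imaging as a ground for removal.
- **Similar number.** This might be read as subsampling the reference period, but the same sentence explains it as the previous six months.

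A statistical analysis plan could define analysis sets. Eligibility, replacement and the reference group are, however, already fixed here, and fixed unevenly.

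**Conclusion.** The concern holds in limited form. Followed as written, the protocol compares CT proportions on different denominators, because sampling, venipuncture and replacement rules shape the new-period group and cannot act in the same way on a reference group defined only by attendance for mTBI. Part of that selection depends on CT use.

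Neither the sign nor the size of the bias can be derived from the document. With 5-10% unsampled, the illustration gives shifts of 1.3 to 3.3 points, below sampling error. At 15% it gives −4.4 or +5.3 points, slightly beyond the ±4.0 points expected from chance. These figures rest on an assumed 70% CT rate, assumed unsampled shares and assumed CT rates of 95% or 40% among the unsampled. It should be corrected because a principal objective is affected and the remedy is cheap. The sampled cohort remains the right one for diagnostic performance.

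**What to change.** - For CT use, costs and times, identify both cohorts with one health-record rule applied unchanged to both six-month windows: adults, the same diagnostic codes, GCS 13-15, injury within 12 hours, and the same exclusions other than those that concern sampling.
- Include every patient so identified, regardless of blood sampling, form completion or the Section 6.1 exclusions.
- State when the unified code and the form came into use. If they did not cover the whole reference window, use the earlier code set in both periods.
- Keep the sampled cohort for diagnostic performance only.
- Reconcile the imaging wording of the sampling criterion in Sections 1 and 4.1.

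The cost is protocol wording and one extra query. The estimated CT reduction may turn out less favourable. If GCS or time of injury was not recorded in structured fields during the reference window, some record review may also be needed.

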## 7. STATISTICAL CONSIDERATIONS

### 7.1. SAMPLE SIZE

The primary endpoint of the study is to replicate the diagnostic performance of the VIDAS TBI assay to predict whether the tested patient would be positive or negative from brain injury visible on head CT scan and to determine that implementation of the VIDAS TBI, in the standard of care of patients with mTBI, is not associated with serious side effects during the six-month period of the study. We expect to test during a six-month period around 1000 patients (from the 3500 patients with suspected TBI that are admitted to our hospital yearly approximately (data from discharge diagnosis of patients with TBI related diagnostic codes)). With this sample size and with an expected prevalence of 10% of CT positivity we expect to have at least 100 patients with positive CTs. With this sample size we expect to replicate the NPV of the BRAINI study with an expected lower bound of the 2-sided 95% CI greater than or equal to 97.0%.

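### The analysis cohort is identified from a diagnosis code plus a form that are not tied to a time before the CT result or reconciled with the patients tested, so CT-positive or deteriorating patients may be missed

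*Protocol*

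**What the plan says.** Intended entry to the study is clinical and takes place at the emergency visit. Under section 5.1, "all patients with mTBI admitted to the ER of the study site and answering to inclusion and exclusion criteria of the study will be considered". Under section 5.2, patients with a GCS of 13 to 15 "will receive a blood test for biomarker determination upon admission".

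The route into the dataset is described separately. Section 5.3.3 reports that "the mTBI diagnostic code was unified and codified (SNOMED CT) and a form was created with the questions that are asked when attending a patient". It goes on to state the rule for finding the cohort: "The completeness of the defined diagnosis together with the designed form will allow the identification of the cohort of patients with mTBI". Section 5.2 adds: "Data will be collected directly from a specified structured form in the electronic health record of the patient".

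Two later steps rest on this extraction:
- The 10-day check of neurological status, hospitalisation and new ER contacts: "This review will be done thanks to the previous automatic extraction of the mTBI data collected in the EHR".
- The analysis database: at the end of section 5.3.3, "the de-identified data from the mTBI cohort will be obtained and transferred into a web based electronic CRF".

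The protocol does not say at what point in the episode the code is assigned or the form completed. It does not say whether a patient recorded under a specific lesion is also captured. It describes no comparison of the extracted cohort with biomarker results, triage records or CT lists.

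**The concern.** In a diagnostic-accuracy study, entry should depend only on information available before the reference standard is known. Here the eligibility criteria meet that condition, but the extraction rule is not bound to it. A diagnosis entry may be made or changed once the CT has been read. If a tested patient with a subdural haematoma or contusion is recorded under that lesion and not under the mTBI code, the extraction could miss that patient. The same could happen to a patient who deteriorates, or whose form was left incomplete.

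Loss of this kind would not be neutral:
- Fewer CT-positive patients means a lower observed prevalence and fewer false negatives, hence a higher NPV.
- Missing patients who deteriorate lowers the deterioration proportion, the second principal outcome measure.
- Sensitivity becomes less precise. It is biased only if the chance of being lost also depends on the test result.

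The first two effects favour the test, in a study meant to establish both its rule-out performance and the safety of the pathway.

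**Working it through.** **The protocol's own figure.** Section 7.1 expects about 1000 tested patients and 10% CT positivity: 1000 × 0.10 = 100 CT-positive patients. This reproduces. The paired expectation, a lower bound of the two-sided 95% CI for the NPV of at least 97.0%, cannot be reproduced, because no expected NPV, sensitivity, specificity or number of test-negative patients is given. The counts below are therefore assumptions.

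**Formula.** With TN true negatives and FN false negatives, n = TN + FN and NPV = TN/n. The exact (Clopper-Pearson) lower bound is the 0.025 quantile of the Beta(TN, FN + 1) distribution.

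**How few false negatives decide the result.** A lower bound of 97.0% needs at least 122 test-negative patients with no false negative. It allows at most 1 false negative in 200, 3 in 300, 5 in 400 and 7 in 500.

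**Effect of losing one false negative.** The assumed specificities of 0.30, 0.40 and 0.50 among 900 CT-negative patients give 270, 360 and 450 true negatives. The false-negative counts are chosen at the boundary, to show how sensitive the bound is there.

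| TN (assumed) | FN, complete cohort | Lower bound | FN, one lost | Lower bound |
|---|---|---|---|---|
| 270 | 3 | 96.8% | 2 | 97.4% |
| 360 | 5 | 96.8% | 4 | 97.2% |
| 450 | 7 | 96.9% | 6 | 97.2% |

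**Effect of losing a share of all CT-positive patients, whatever their test result.** Assume sensitivity 0.97 and specificity 0.30. With a share f lost, 100 × (1 − f) CT-positive patients remain, FN = 3 × (1 − f) and TN = 270. Fractional FN are expected values.

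| Share lost (assumed) | CT-positive left | Observed prevalence | NPV | Lower bound |
|---|---|---|---|---|
| 0% | 100 | 100/1000 = 10.0% | 98.9% | 96.8% |
| 10% | 90 | 90/990 = 9.1% | 99.0% | 96.98% |
| 30% | 70 | 70/970 = 7.2% | 99.2% | 97.3% |
| 50% | 50 | 50/950 = 5.3% | 99.4% | 97.7% |

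**Sensitivity.** If loss is unrelated to the test result, expected sensitivity is unchanged and only the interval widens: the lower bound is 91.5% for 97/100 and 86.3% for 48/50.

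**The case against.** A reader might infer that CT-positive patients do drop out of the primary analysis. The documents do not support that, and several points speak against it:
- Nothing says that the code is set after the CT, that a lesion code replaces it, or that an incomplete form excludes a patient. The form holds the questions asked when the patient is seen, which suggests attendance data.
- Section 7.1 does mention "data from discharge diagnosis of patients with TBI related diagnostic codes", but this explains the yearly volume estimate. It does not describe the study extraction, and section 5.3.3 says the code has since been unified.
- Mild TBI is defined by GCS (sections 2.1 and 4.1), so a lesion on CT does not move a patient out of the category.
- The planned dashboard reports pathologic CTs by biomarker result, and section 7.1 expects at least 100 positive CTs. CT-positive patients are plainly meant to be in the cohort.
- Regular quality checks on the record are planned, and code lists and queries may be set out in documents not at hand.

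All of this stands against the strong reading. It does not remove the narrower point. The quality checks concern what physicians enter in the record, and no search for tested patients absent from the cohort is described. That some CT-positive patients are expected does not show that all are captured. The rule is also stated in the protocol and feeds the database and the 10-day review, so it is more than a detail left open.

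Two further objections hold. The counts in the first table were placed near the threshold, and 97.0% is an expected bound in section 7.1, not a declared success criterion. A frame built on test results also has no counterpart in the previous six months, which limits where it can be used.

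**Conclusion.** The point holds as a risk that the protocol leaves open, not as a demonstrated loss. Cohort identification rests on a code and a form that are neither tied to a time before the CT result nor reconciled with the patients tested. If patients are lost in relation to the CT result or later deterioration, prevalence and the deterioration proportion are understated and the NPV overstated.

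The size cannot be derived from the documents. Under the assumed counts, one lost false negative near the boundary moves the lower bound by about 0.3 to 0.6 percentage points and across 97.0%. Losing 10% of CT-positive patients at random with respect to the test moves it by under 0.2 points (96.8% to 96.98%), and losing half moves it by under 1 point (96.8% to 97.7%). A bias in sensitivity should not be claimed unless loss depends on the test result. The change is worth making because the safeguard is cheap and would show directly whether the problem exists.

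**What to change.** Amend section 5.3.3 as follows:
- **Accuracy and deterioration analyses.** Take as the frame all patients with a VIDAS TBI result in the laboratory system during the six months. Apply the eligibility criteria from admission data (GCS, time of injury, mechanism), whatever the final diagnosis code or form completion. Use the code and form to supply variables, not to decide entry. Run the 10-day review on the same list.
- **Reporting.** State how many tested patients lack the code, the form or both, if possible by CT result.
- **CT-reduction, time and cost comparisons with the previous six months.** No VIDAS result exists in that period, so keep one ascertainment rule and apply it identically to both periods.

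The cost is one laboratory query, a change of wording, and some record review to complete missing form fields. Patient care is not affected.
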